### **3.2 Exclusion Criteria**

Histologies of myeloma or lymphoma

Candidates planned for surgical decompression

Spine instability as determined by SINS score >12 [15]

Compression fracture identified by > 50% loss of vertebral body height

Bony retropulsion at the index spine as predominant cause of epidural extension or cord compression

Prior radiation to the spinal cord at the index spine where the composite dose (including study treatment) would exceed documented constraints

## 4.0 STUDY DESIGN

### 4.1 General Design

#### *Treatment*

This will be a pilot study assessing the feasibility of staged radiotherapy and adaptive planning on the management of inoperable epidural extension or spinal cord compression (documented by diagnostic imaging). All patients should be started on dexamethasone unless medically contraindicated and dosed per institution guidelines. Initial treatment after evaluation and registration will consist of an initial fraction of 8-24 Gy delivered using a SBRT or 3D conformal approach to the affected region(s). The patients will be re-imaged within 14-21 days by the same modality as diagnosis to assess for radiographic response. If feasible, a second fraction will be delivered at this point per discretion of the treating physician.

#### *Follow-up*

Patients will be evaluated with a history, physical examination, pain score, and neurologic assessment at each treatment visit by the treating physician, or more frequently as clinically indicated. Interval diagnostic imaging will be completed 14-21 days after initial treatment to assess response. Thereafter, a third set of diagnostic images will be obtained at 8-10 weeks following initial treatment. Patients will be followed thereafter by the treating physician for survival and recurrence as clinically indicated.

## 4.2 Study Calendar

	Screening		Treatment	Post-Treatment	
	Day -21 to -1	Day -7 to -1	Day 1	Day 14-21	Week 8-10
History		X		X	X
Physical Exam		X		X	X
SINS Score		X			
Vital Signs & Weight		X		X	X
Neurologic Evaluation		X A		X	X
NRPS		X		X	X
ECOG PS		X		X	X
FACT-G		X		X	X
Pregnancy Test		X			
Diagnostic Imaging	X			X	X C
Radiation Therapy			X	X B	

A Appendix D: Neurologic and Functional Assessment.

B If indicated, a second fraction will be delivered at this point at the discretion of the treating physician.

C should 810Follow-up imaging thereafter should occur at the discretion of the treating physician.

### 3. Primary Endpoint

The primary endpoint of this study is the radiographic response of the spinal tumor, as measured by:

Distance between the gross disease and spinal cord  $\geq$  3mm after treatment.

A reduction in the epidural tumor volume or thecal sac compression by  $\geq$  10% after treatment

### 4.4 Secondary Endpoints

Pain control: Pain scores as measured by the Numerical Rating Pain Scale (NRPS) estimation

Quality of Life: Scores from Functional Assessment of Cancer Therapy (FACT-G)

Ambulation: Based on ambulation score and standardized neurologic exam (Appendix D)

Progression-free survival: the interval from study registration to date of disease progression or death, censored at the date of data collection

Overall survival: the interval from study registration to death, censored at the date of data collection

Grade  $\geq$  2 radiation-induced lung toxicity, scored using CTCAE, v. 4

Any grade  $\geq$  3 treatment-related toxicity, scored using CTCAE, v. 4

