More recently, a prospective clinical trial reported on the effectiveness of SBRT for patients with MESCC, as measured by the reduction of epidural tumor volume and improvement in thecal sac patency. They enrolled 62 patients with MESCC who were treated with 14-20 Gy in a single fraction. The results demonstrated a 64% reduction of the epidural tumor volume at 2 months following treatment, with 80% of the patients also showing improvement in thecal sac patency. Notably, however, 16% of these patients had neurologic progression (9/62 patients). Of these 9 patients, 5 had decompressive surgery thereafter in which 2 showed necrosis, 2 died from intraoperative complications and 1 had tumor progression [12]. This trial indicated that a radiographic response can be observed rapidly, however there is clearly a risk of neurological toxicity from delivering single doses of 14 Gy or higher to tumors abutting the spinal cord.

Previous studies have estimated spinal cord constraints ranging from 10-14 Gy for single fraction SBRT treatments [10, 13, 14]. RTOG 0631, an ongoing prospective randomized trial which investigated the use of SBRT for palliation of spine metastases (16 Gy SBRT vs. 8 Gy x 1 conventional), applied these constraints using 10 Gy to 10% of the spinal cord (cross sectionally) to a maximum of 6mm above and below the target volume, and max dose of 14 Gy. However, patients are excluded if there was frank epidural compression within 3 mm of the spinal cord.

Based on the above findings, we are proposing a trial for patients with inoperable MESCC utilizing adaptive planning and a staged application of radiotherapy. Such an approach can potentially deliver therapeutic doses to the tumor while respecting the established spinal cord constraints. We hypothesize that a single fraction of treatment may induce a short-interval radiographic response (within approximately 2-3 weeks), which can then be used to plan an additional treatment if needed. The response may

also allow us to achieve therapeutic dose levels by reducing the volume of overlap with the spinal cord. We will also observe the radiographic response from high-dose single fraction regimens if decompression can be achieved in this fashion.

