## 5.0 RADIOTHERAPY

### 5.1 Dosimetry

All patients will receive a first fraction of 8 to 24 Gy using a 3D or SBRT technique. The second treatment will be at the discretion of the treating physician and will be based on the clinical parameters, diagnostic interval imaging (2-3 weeks), and achievement of spinal cord dose constraints as described below.

The spinal cord constraints for the first fraction will be a maximum of 9Gy to less than 0.01 cc and 8Gy to less than 0.1 cc volume, respectively. Composite dose constraints(combining both treatments) for the spinal cord area maximum of 18 Gy to less than 0.01 cc and 16 Gy to less than 0.1 cc and respectively. Every effort will be made to plan for 90% composite target coverage while keeping the spinal cord dose limits."

If considering a larger single fraction dose (14-16 Gy or above), the constraint should be 12 Gy to less than 0.01cc

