## 10.0 DATA SAFETY AND MONITORING BOARDS

The Albert Einstein College of Medicine/Albert Einstein Cancer Center Data Safety Monitoring Committee (DSMC) has the responsibility for ensuring data and safety monitoring along with the PI who is ultimately responsible for the ongoing monitoring and safety of clinical protocols. The primary functions of the AECC DSMC are as follows:

1. To review and ensure protocol compliance with dose escalation in phase I trials
2. To review/assure protocol compliance for all trials that have two-stage phase II designs,
3. Reviewing all internal and external serious adverse reports, investigator alerts, action letters, and other safety reports for trials being performed at AECC-affiliated institutions and;
4. To implement and to determine the adequacy of DSM plans of all approved protocols.

The DSMC is an independent committee and meets on a monthly basis. During its monthly meeting, the DSMC will review serious (grade 3 or higher) adverse events from this study. In the event that the DSMC decides that a revision is warranted, the committee will immediately notify the principal investigator of this study. The DSMC has the authority to close trials to patient accrual should the risk to patients be excessive or outweigh the potential benefits of the study. All study suspensions and closures will be forwarded to the IRB/CCI and study sponsor from the DSMC.

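### Among the CTCAE toxicity endpoints in 4.4, only lung is counted at grade ≥2; spinal cord toxicity, the hazard named in 2.3, is counted only at grade ≥3 and if judged treatment-related

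*Combined protocol and SAP*

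**What the plan says.** Section 4.4 scores toxicity by CTCAE v4 in two lines. The first is grade ≥2 "radiation-induced lung toxicity, scored using CTCAE, v. 4". The second covers any organ, but only at grade ≥3 and only for "treatment-related toxicity, scored using CTCAE, v. 4". Neither line names the spinal cord, and no myelopathy endpoint is defined elsewhere.

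The same list has an Ambulation endpoint based on the ambulation score and the Appendix D neurologic examination (strength, sensation, continence, sphincter tone, mobility class I to IV). It has no grade cut-off and no attribution test. It also gives no direction or size of change, no time point and no denominator. Section 7.1 adds only that secondary endpoints are reported descriptively.

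On the hazard, Section 2.3 says that "there is clearly a risk of neurological toxicity from delivering single doses of 14 Gy or higher to tumors abutting the spinal cord". Section 5.1 states: "All patients will receive a first fraction of 8 to 24 Gy using a 3D or SBRT technique". The same section limits the cord maximum (to less than 0.01 cc) to 9 Gy in the first fraction, 12 Gy when a larger single fraction is considered, and 18 Gy for both treatments combined.

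On oversight, Section 10.0 says that at its monthly meeting "the DSMC will review serious (grade 3 or higher) adverse events from this study".

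**The concern.** The lower reporting threshold goes to lung, while the organ whose tolerance drives the staged design falls under the general line. Two kinds of neurologic harm then fall outside both toxicity rates: a grade 2 cord event, and a decline of any grade that the investigator attributes to tumor.

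The attribution condition matters because cause is hard to settle in this disease. For the patients with neurologic progression in the MESCC radiosurgery trial cited in 2.3, the protocol reports: "Of these 9 patients, 5 had decompressive surgery thereafter in which 2 showed necrosis, 2 died from intraoperative complications and 1 had tumor progression". A cord-directed safety figure that depends on a treatment-related judgement can therefore miss part of the harm. A reader of the pilot report would find a grade ≥2 rate for lung and no matching figure for the cord. That figure would be wanted when the larger study foreseen in 7.1 is planned.

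**Working it through.** **1. Which events enter which endpoint (4.4 and 11.0)**

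| Event | Grade ≥2 lung line | Grade ≥3 related line | Ambulation / AE listing |
|---|---|---|---|
| Grade 2 pneumonitis, radiation-induced | yes | no | AE listing |
| Grade 2 cord event, related | no | no | yes, no defined count |
| Grade ≥3 neurologic decline, attributed to tumor | no | no | yes, no defined count |
| Grade ≥3 cord event, related | no | yes | yes |

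The gap is in the middle two rows.

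**2. The protocol's background rate (2.3).** The text prints 16% beside 9 of 62 patients. 9/62 = 14.5%, so the percentage and the fraction do not quite agree. I use 9/62 and show 16% as well.

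**3. How much attribution can move a rate.** An operative finding is given for 3 of the 9 patients: 2 necrosis and 1 tumor progression. Assume that necrosis counts as a treatment effect. The treatment-attributed rate then lies between 2/62 = 3.2% (only those two) and 8/62 = 12.9% (all but the tumor case). The attribution-free rate is 14.5%.

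**4. Chance of at least one event, 1 − (1 − p)^n**

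| Rate p | n = 15 (Schema) | n = 24 (Section 7.1) |
|---|---|---|
| 5% (assumed) | 1 − 0.95^15 = 54% | 71% |
| 9/62 | 1 − (53/62)^15 = 90% | 98% |
| 16% (as printed) | 1 − 0.84^15 = 93% | 98% |

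Expected events with 15 patients: 15 × 0.05 = 0.75; 15 × 9/62 = 2.2; 15 × 0.16 = 2.4. The 9/62 comes from patients given 14-20 Gy in one fraction. This trial also allows 8 Gy, 3D technique and the cord limits of 5.1, so the lower rate is a fair counterweight.

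**5. Precision (Clopper-Pearson, 95%).** 0/15: 0 to 21.8%. 2/15: 1.7% to 40.5%. 0/24: upper limit 14.2%.

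**6. Deaths and the denominator.** Section 2.1 gives a median survival of 3-6 months. Week 10 is 2.30 months. Under an assumed exponential curve, deaths by week 10 are 1 − 2^(−2.30/3) = 41% (6.2 of 15) or 1 − 2^(−2.30/6) = 23% (3.5 of 15). Suppose 2 of 15 patients worsen and both survive to be examined. The all-treated figure is 2/15 = 13.3%. If 4 or 6 others die unexamined, the figure among those examined is 2/11 = 18.2% or 2/9 = 22.2%. Counting unexamined deaths as non-events pulls the all-treated figure down.

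**The case against.** The strongest reply is that neurologic decline is already an endpoint. Objective 1.2 calls for neurologic examinations before and after treatment, 4.4 lists Ambulation, 6.2 ties it to Appendix D, and the 4.2 calendar schedules the evaluation at baseline, day 14-21 and week 8-10. This stands. A reader might infer that lesser cord injury goes unrecorded; the documents do not support that, and 11.0 records all adverse events whether or not related. What the reply does not supply is a definition of worsening. A mean score or a before-and-after table would satisfy the Ambulation line, and patients who improved could then offset those who declined.

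Three other strong readings should also be set aside.

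- **That the cord may receive 24 Gy.** The 8-24 Gy range is the fraction dose. Section 5.1 limits the cord to 9 Gy or 12 Gy in a single fraction.
- **That the DSMC sees nothing below grade 3.** Section 10.0 also has it review serious adverse event reports. Section 11.1 defines seriousness by outcome, including disability, and 11.2 requires reporting within 24 hours even when an event seems unrelated.
- **That 11.2 removes neurologic decline due to tumor.** It exempts SAEs clearly caused by progression, yet also asks for any SAE regardless of apparent relation. That is ambiguous, not a clear exclusion.

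It can also be said that this is a descriptive pilot without hypothesis tests, so no stated decision depends on the count. That is true, and it limits the weight of the point. But a descriptive safety report still needs a defined quantity, and the plan already provides one for lung.

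**Conclusion.** The point holds in a limited sense. Among the toxicity endpoints, the cord is counted only at grade ≥3 and only if treatment-related, while lung is counted from grade 2. Neurologic decline that is milder or attributed to another cause is left to the Ambulation examination and the AE listing, without a defined count.

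The count would probably not be empty: the chance of at least one event with 15 patients is 54% to 90%, depending on whether an assumed 5% or the cited 9/62 applies. It would describe the risk and not settle it, as the interval for 2/15 shows. The conclusion on the text does not depend on whether the trial enrolls 15 patients (Schema) or 24 (7.1). The event probabilities assume independent patients and a transferable rate, and the death figures assume an exponential curve.

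This is a modest improvement to consider. It is not evidence that safety monitoring is absent.

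**What to change.** Keep the lung line and add to 4.4: number and proportion of treated patients with a new or worsened grade ≥2 CTCAE v4 spinal cord or neurologic adverse event, or worsening of at least one Appendix D mobility class from baseline, by week 8-10, whatever the attribution, with the attributed cause listed for each event and a Clopper-Pearson 95% CI. Name the CTCAE terms that count.

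Report the proportion both among all treated patients and among those examined at each visit. List deaths and missed examinations separately. Report changes in motor grade descriptively.

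Optionally, attach the Appendix D footnote in the 4.2 calendar to the two follow-up cells as well. This only clarifies, because 6.2 already specifies Appendix D.

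The cost is one endpoint line, with no added visits or instruments. The drawbacks are that some tumor-progression and steroid effects will be counted (hence the listed cause), a patient at mobility class IV at baseline cannot worsen on that score, scheduled examinations end at week 10 and will miss later myelopathy, and the interval will be wide.

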## 5.0 RADIOTHERAPY

### 5.1 Dosimetry

All patients will receive a first fraction of 8 to 24 Gy using a 3D or SBRT technique. The second treatment will be at the discretion of the treating physician and will be based on the clinical parameters, diagnostic interval imaging (2-3 weeks), and achievement of spinal cord dose constraints as described below.

The spinal cord constraints for the first fraction will be a maximum of 9Gy to less than 0.01 cc and 8Gy to less than 0.1 cc volume, respectively. Composite dose constraints(combining both treatments) for the spinal cord area maximum of 18 Gy to less than 0.01 cc and 16 Gy to less than 0.1 cc and respectively. Every effort will be made to plan for 90% composite target coverage while keeping the spinal cord dose limits."

If considering a larger single fraction dose (14-16 Gy or above), the constraint should be 12 Gy to less than 0.01cc

### 5.2 CT simulation, Immobilization and Patient setup

Computed tomography will be the primary image platform for targeting and treatment planning. The planning CT scans should be performed without IV contrast, however may be preceded with a CT myelogram where possible to accurately delineate the spinal cord. Oral contrast may be given. Axial acquisitions with gantry 0 degrees will be required with spacing 1.25-2.5 mm between scans in the region of the tumor. Images will be transferred to the treatment planning computers for treatment planning.

Patients must be positioned in a stable supine position capable for reproducibility of positioning and immobilization from simulation to treatment, allowing the patient to feel as comfortable as possible. The arms should be positioned based on treatment location. Positions uncomfortable for the patient should be avoided to prevent unnecessary movement. A prone position is not allowed. A vacuum bag should be used for immobilization or for cervical spine or cervicothoracic junctional areas, a rigid head and neck immobilization device should be used.

Verification CT scans or portal films prior to each treatment should be taken.

### 5.3 Target Volumes and Coverage

Image fusion between MRI (gadolinium contrast T1-weighted and T2-weighted images) and simulation CT is recommended for delineation of both the soft tissue tumor

component and the spinal cord. If possible, CT myelogram should be obtained prior to simulation for accurate delineation of the true cord. Special attention (and consideration of deformable registration) should be taken with image fusion when simulation CT and MRI images are taken in different imaging positions.

The gross tumor volume (GTV) should include only the gross disease visible on pre-treatment imaging. A 0-3mm margin expansion is allowed to clinical target volume (CTV), as well as a further 1-2 mm expansion to planning target volume (PTV).

For 3D treatment, the target volume should also be delineated. The treatment field can include a margin of 1-2 cm beyond the vertebral body(s) in any direction, based on the treating physician's discretion, as long as more than or equal to 90% of the target spine volume is covered by the prescription dose.

#### **5.4 Critical Structures**

Lung, true cord, esophagus, larynx, brachial plexus, heart/pericardium, kidneys, bowel and liver should be included based on the location of the spinal lesion, and contoured on the published atlases available on the RTOG web site. All critical structures will be outlined as detailed in the RTOG 0631 protocol. (<http://www.rtog.org/CoreLab/ContouringAtlases.aspx>). Dosimetric constraints for organs at risk are listed in **Table 2**. These have been adopted from RTOG 0631.

Cauda Equina	<0.03 cc <5 cc	16 Gy 14 Gy	neuritis
Sacral Plexus	<0.03 cc <5 cc	18 Gy 14.4 Gy	neuropathy
Esophagus*	<0.03 cc <5 cc	16 Gy 11.9 Gy	stenosis/fistula
Ipsilateral Brachial Plexus	<0.03 cc <3 cc	17.5 Gy 14 Gy	neuropathy
Heart/Pericardium	<0.03 cc <15 cc	22 Gy 16 Gy	pericarditis
Great vessels*	<0.03 cc <10 cc	37 Gy 31 Gy	aneurysm
Trachea* and Larynx	<0.03 cc <4 cc	20.2 Gy 10.5 Gy	stenosis/fistula
Skin	<0.03 cc <10 cc	26 Gy 23 Gy	ulceration
Stomach	<0.03 cc <10 cc	16 Gy 11.2 Gy	ulceration/fistula
Duodenum*	<0.03 cc <5 cc	16 Gy 11.2 Gy	ulceration
Jejunum/Ileum*	<0.03 cc <5 cc	15.4 Gy 11.9 Gy	enteritis/obstruction
Colon*	<0.03 cc <20 cc	18.4 Gy 14.3 Gy	colitis/fistula
Rectum*	<0.03 cc <20 cc	18.4 Gy 14.3 Gy	proctitis/fistula
Renal hilum/vascular trunk	<2/3 volume	10.6 Gy	malignant hypertension
Parallel Tissue	Critical Volume (cc)	Critical Volume Dose Max (Gy)	Endpoint (<math>\geq</math> Grade 3)
Lung (Right & Left)	1000 cc	7.4 Gy	Pneumonitis
Renal cortex (Right & Left)	200 cc	8.4 Gy	Basic renal function

\*Avoid circumferential irradiation

Table 2 – Dosimetric Constraints

## 5.5 Radiotherapy Adverse Events

Reversible or permanent alopecia, bone marrow toxicity, skin pigmentation, and esophagitis are expected side effects of radiation therapy. Radiation induced myocarditis or transverse myelitis rarely occur when the pericardium and spinal cord receive doses lower than 50 Gy. Radiographic evidence of radiation change and subsequent fibrosis of the lung will occur within lung volume receiving  $\geq$  20 Gy, usually within the

first six months after initiation of treatment. It is essential to spare as much normal lung as possible in order to avoid symptomatic lung injury.

## 6.0 RESPONSE ASSESSMENT

### 6.1 Primary Endpoint – Radiographic Response

The primary endpoint of this study is achieving radiographic response in the metastatic spinal lesion.

Radiographic response will be achieving 3mm in shortest distance axially between the gross disease and spinal cord at the level where the most severe compression was present, between pre-treatment and interval imaging scans.

Radiographic response will also be achieving a 10% reduction in epidural tumor volume or thecal sac compression between pre-treatment and interval imaging scans. Epidural tumor volume will be estimated by using target volumes contoured before and after treatment by the same practitioner. Thecal sac compression will be estimated using a method adapted from [12]. The thecal sac area at the level of compression is compared to the average value of thecal sacs measured at 1 vertebral body above and below this level. One minus the ratio of the compressed to normal thecal sac area will provide an estimate of the thecal sac compression. These measurements will be taken at the same spine levels to maintain consistency.

Response assessments will be completed by an attending radiation oncologist not directly involved in the patient's clinical care. This approach will preserve objectivity and mirrors an existing peer review process in place for all standard and stereotactic radiation treatments. Collaboration with neuroradiology will also be encouraged during these assessments.

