### 6.2 Secondary Endpoints – NRPS, FACT-G, Ambulation

Secondary endpoints include pain, quality of life and functional outcomes.

For evaluation of pain relief, the Numerical Rating Pain Scale will be used, as done in RTOG 0631. The NRPS is a measure of pain on an 11-point scale (0-10) and has been validated previously on similar cohorts [16].

For quality of life, the Functional Assessment of Cancer Therapy (FACT-G), v. 4.0, also will be collected (also utilized in RTOG 0631). The FACT-G is a commonly used tool measuring quality of life from 4 different perspectives (physical, social, emotional and functional) [17]. It is completed quickly, is accessible to those with varying educational backgrounds, and is available in many languages ([http://www.facit.org/translation/translation\\_landing.aspx](http://www.facit.org/translation/translation_landing.aspx)).

Functional outcomes and ambulation will be assessed by standard neurologic assessment (Appendix D) by the treating physician.

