## 7.0 STATISTICAL CONSIDERATIONS

### 7.1 Data Analysis

This pilot study will yield preliminary data on the primary endpoint of distance between gross disease and spinal cord of at least 3mm. Data from the study will be summarized using standard descriptive statistics; formal hypothesis testing will not be performed. Estimates of the treatment effect and standard error on the number of subjects achieving  $\geq 3$  mm distance will also be used to determine the sample size required for the larger scale study. Therefore, the size of the pilot study should be sufficient to produce reasonably precise estimates of these parameters, where precision is measured by the width of the 95% confidence interval.

The treatment effect will be estimated by  $p$ , the observed proportion of patients achieving at least 3 mm distance from the gross disease and spinal cord. Confidence intervals for the true proportion will be computed using Clopper-Pearson exact confidence interval. With 24 subjects and assuming an expected response rate  $p = 50\%$  produces a two-sided 95% confidence interval with a width equal to 58% (i.e.  $21\% \leq p \leq 79\%$  ). The width shows that the response rate will not be lower than 20%. Since this is a feasibility, study no power calculation is done.

Data regarding secondary endpoints will be reported in a descriptive manner.

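### Sections 6.1 and 7.1 define the primary endpoint differently, so the same scans can give two primary response rates

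*Combined protocol and SAP*

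**What the plan says.** Section 1.1 puts three measurements under the primary objective (tumor-to-cord distance, epidural tumor volume and extent of epidural compression), each before and after treatment, and does not rank them.

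The Primary Endpoint section, printed between 4.2 and 4.4, names radiographic response and gives two criteria for it. One is a distance of at least 3 mm. The other reads "A reduction in the epidural tumor volume or thecal sac compression by" at least 10%. No connective joins the two.

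Section 6.1 makes radiographic response the primary endpoint, defines it first by the 3 mm distance at the most compressed level, and continues: "Radiographic response will also be achieving a 10% reduction in epidural tumor volume or thecal sac compression between pre-treatment and interval imaging scans".

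Section 7.1 is narrower: "This pilot study will yield preliminary data on the primary endpoint of distance between gross disease and spinal cord of at least 3mm". It defines the treatment effect p as "the observed proportion of patients achieving at least 3 mm distance from the gross disease and spinal cord", gives it a Clopper-Pearson interval, and uses it to size the larger study. It does not mention the 10% criterion.

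The secondary lists do not take up the other two measures. Section 6.2 says "Secondary endpoints include pain, quality of life and functional outcomes". Section 4.4 begins with "Pain control: Pain scores as measured by the Numerical Rating Pain Scale (NRPS) estimation" and goes on to quality of life, ambulation, progression-free and overall survival, and toxicity.

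The assessment time is not in dispute. Section 4.1 states: "Interval diagnostic imaging will be completed 14-21 days after initial treatment to assess response".

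**The concern.** Two sections each say what the primary endpoint is, and they do not say the same thing. A patient whose epidural volume falls by 10% or more, but whose tumor remains less than 3 mm from the cord, meets a response criterion in 6.1 and fails the only criterion in 7.1.

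The planned output of this single-arm pilot is one proportion with an interval, so the responder definition determines the result. If it stays open, the definition could be settled after the scans have been read. The rate reported as primary could also differ from the p that 7.1 carries into the design of the larger study.

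**Working it through.** **Step 1. The plan's own figure.** Inputs from section 7.1: 24 subjects, expected rate 50%, two-sided 95% Clopper-Pearson interval. Formula: lower limit = 0.025 quantile of Beta(x, n − x + 1); upper limit = 0.975 quantile of Beta(x + 1, n − x). With x = 12 and n = 24 this gives 29.1% to 70.9%, a width of 41.8 points. Section 7.1 states 21% to 79%, a width of 58 points. That matches 6 of 12 (21.1% to 78.9%, width 57.8) and not 12 of 24. This is a separate error, and the present point does not depend on it.

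**Step 2. Where the rules part.** Sort the N patients by what the interval scan shows:

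| Interval scan | Number | 7.1 (distance only) | 6.1 as OR | 6.1 as AND |
|---|---|---|---|---|
| Both criteria met | a | responder | responder | responder |
| 3 mm only | b | responder | responder | non-responder |
| 10% only | c | non-responder | responder | non-responder |
| Neither | d | non-responder | non-responder | non-responder |

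Rate under 7.1 = (a + b)/N. Rate under OR = (a + b + c)/N, which exceeds it by c/N and can never be lower. Rate under AND = a/N, which falls short of it by b/N and can never be higher. OR is the natural reading of 6.1, but the direction of the difference depends on it.

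**Step 3. Size per discordant patient.** 1/15 = 6.7 points (N = 15, Schema). 1/24 = 4.2 points (N = 24, section 7.1). Both are shown because the documents give both sample sizes.

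**Step 4. Illustration under OR.** The documents do not give c. Taking c = 1 to 3 purely as an example, and starting from the 50% assumed in 7.1 (7 or 8 of 15, or 12 of 24), with 95% Clopper-Pearson limits:

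| Rate under 7.1 | c = 1 | c = 2 | c = 3 |
|---|---|---|---|
| 7/15 = 46.7% (21.3–73.4) | 8/15 = 53.3% (26.6–78.7) | 9/15 = 60.0% (32.3–83.7) | 10/15 = 66.7% (38.4–88.2) |
| 8/15 = 53.3% (26.6–78.7) | 9/15 = 60.0% (32.3–83.7) | 10/15 = 66.7% (38.4–88.2) | 11/15 = 73.3% (44.9–92.2) |
| 12/24 = 50.0% (29.1–70.9) | 13/24 = 54.2% (32.8–74.4) | 14/24 = 58.3% (36.6–77.9) | 15/24 = 62.5% (40.6–81.2) |

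Under AND the movement is downward. From 8/15 with b = 2, the rate is 6/15 = 40.0% (16.3–67.7). From 12/24 with b = 3, it is 9/24 = 37.5% (18.8–59.4).

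**Step 5. Range if the 10% criterion is common.** Let q be the probability of meeting the 10% criterion. The documents do not give it; assume 50% to 90%, with the 3 mm rate held at 50%.

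- OR, criteria independent: 1 − 0.5(1 − q) = 75% to 95%.
- OR, criteria nested: max(0.5, q) = 50% to 90%.
- AND, criteria independent: 0.5q = 25% to 45%.
- AND, criteria nested: min(0.5, q) = 50%.

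The nearest figures in the documents are in section 2.3: in an earlier trial, epidural volume fell by 64% at 2 months and 80% of patients had improved thecal sac patency. They come from a later time point and do not use a 10% threshold, so they make discordant patients plausible without saying how many to expect at 14–21 days.

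**The case against.** The best defence is that 7.1 is clear in itself. It prespecifies one proportion, one interval and one use for the result, in a descriptive pilot with no hypothesis test. On this view 6.1 merely describes two primary measures to be reported side by side, and the distance is the one chosen for the interval.

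Part of this stands. The wording of 6.1 does not strictly say that either criterion suffices. The two rates coincide if no patient meets just one criterion. Nor is 7.1 plainly the version to keep: section 1.1, the Primary Endpoint section and 6.1 all place volume or compression at the primary level.

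The defence does not remove the conflict. No section calls the criteria co-primary, ranks them, or makes the 10% measure supportive. Section 7.1 plans no specific estimate for it; only the general sentence on descriptive statistics could cover it.

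**Conclusion.** The primary endpoint is inconsistently defined and needs correcting. Following 6.1 or 7.1 as written can give different primary proportions from the same patients, by 6.7 points per discordant patient at N = 15 or 4.2 at N = 24. The number of discordant patients is unknown, so the total gap is neither estimated nor bounded here.

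Three stronger readings are tempting, and the documents do not support them:

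- **That 6.1 always gives the higher rate.** This holds only under OR. If both criteria were required, the 6.1 rate would be equal to or below the 7.1 rate.
- **That type I error is inflated.** Section 7.1 rules out formal testing. The harm is an ambiguous primary proportion, a definition open to choice after the scans are read, and an unclear input to the larger study.
- **That almost no patient starts at 3 mm or more, so baseline distance can be ignored.** The checklist in Appendix A requires cord compression, but sections 3.1 and 4.1 also admit epidural extension without it.

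**What to change.** Use one responder definition, assessed on the 14–21 day interval scan, in section 1.1, the Primary Endpoint section, 6.1 and 7.1. The sponsor should choose before scans are assessed.

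**Option A: keep the rule that 7.1 analyses.** Primary response is a shortest axial distance of at least 3 mm between tumor and cord at the level of worst baseline compression. In section 1.1, mark distance as the primary metric. In 6.1, replace the whole sentence that introduces the 10% criterion with: *Changes in epidural tumor volume and in thecal sac compression from baseline to the interval scan will be reported as secondary endpoints.* Keep the measurement methods that follow it. Remove the 10% line from the Primary Endpoint section and add both measures to 4.4 and 6.2.

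**Option B: keep both criteria as primary.** State the connective, or as against and, in the Primary Endpoint section and in 6.1. Rewrite 7.1 so that p, its interval and the sizing of the larger study use that composite, and report the 3 mm proportion beside it.

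Under either option, report how many patients were already at 3 mm or more at baseline. Rules for the denominator or for missing scans are not needed to resolve this conflict and can be settled separately.

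**Cost.** Wording only; section 1.1 already calls for all three measurements before and after treatment. Under Option A the reported rate can be no higher than under an OR rule.
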